However there is a key difference in the clinical populations found in the literature, surgeons have an operative team and are not responsible for patient monitoring while operating. Likewise anaesthetists are usually accompanied by an ODP and are not undertaking practical skills in isolation.

We were not able to find any published literature addressing attention and perception during ICU procedures.

What does this research add?

There is no published experimental data investigating how clinician time perception and attention are impacted by performing tasks in an IC environment. There is an expectation that time perception and attention are preserved, such that clinicians can insert central access as a sole practitioner. Should our investigation show that attention is impacted then this could inform changes to practice as to how monitors and/or additional staff members are utilised during procedures and clinical tasks and how practitioners are trained to undertake them.

AIM(S) OF STUDY

- To investigate the relationship between task type, perceptual loading and attention in an ICU environment
- To investigate the relationship between task type, perceptual loading and time perception in an ICU environment
- To examine if the extent of these effects (if any) are affected by clinician role and/or experience

OBJECTIVES

The objective of this study is to measure clinician awareness of time progression and monitoring trends in the clinical environment during 2 different types of task.

HYPOTHESIS

H₀: Task type has no impact on clinician time perception or awareness of monitoring trends.

H_A: In the technical task clinician time awareness is more inaccurate than in the administrative task

H_B: In the technical task clinician awareness of monitoring trends is impaired compared to in the administrative task

STUDY DESIGN

STUDY SETTING/LOCATION

This will be a single-centre study undertaken in the Intensive Care Units at Great Ormond Street Hospital. The study tasks will be run in the simulation room on the general Paediatric ICU.

STUDY POPULATION

Participants will be recruited from the group of ICU junior/senior tier fellows and Consultants working on the ICUs at Great Ormond Street Hospital. This comprises a pool of around 40 staff members. All staff members are routinely involved in the care of patients in a PIC environment.

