Participants will be recruited through convenience sampling of those working or training on the ICUs on days when it is possible to run the tasks. Individuals will not be recruited more than once.

Each participant will be given a numeric study ID and parameters recorded against this including:

- Job title- Consultant/fellow
- Gender- Male/female/prefer not to say
- Age- 21-30/31-40/41-50/51-60/61+
- Number of CVCs that they have previously inserted - <10, 10-50, >50).
- Time since last simulation training- 1 week/ 2-4 weeks/ 1-2 months / 3-6 months / 7-12 months / 1-2 years / >3 years

STUDY OUTCOMES

Primary Outcomes

Mean and standard deviation (accuracy) of time intervals measured.

Accuracy of retrospective recall of trends in monitored observations.

Secondary Outcomes

Impact of experience on time perception and monitoring changes.

STUDY PROCEDURES

Recruitment of participants

Participants will be provided with the information sheet appended and given the opportunity to ask any questions before consenting to the study. They will be asked to sign the appended consent form. Their consent forms will be in no way linked to the data collected such that participants could be identified from their data.

Randomisation

Block randomisation will be used to ensure even distribution of individuals at each grade of experience between the allocation groups. A block size of 4 will be used with 2 strata (grade= Consultant, Other). The randomisation list was determined by an online randomisation service ^[27]. The list generated is included as an appendix.

Two parts of the experimental process are randomised.

The first is the order in which the administrative and technical tasks are performed- this is randomised to remove the impact of primacy-recency impacts as well as task training through more practice with the timing apparatus.

The second is the scenario displayed on the monitor. As we are asking participants to identify a trend, randomisation to an increasing or decreasing trend reduces the likelihood of guessing the correct answer.

The study cannot be blinded at the time of data capture given the significant obvious differences between the tasks.

Study procedure

Structure

The overall structure is outlined below with further detail on each section provided in the following section.

Section order	Comment
Consent and discussion	To ensure valid consent and answer queries

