Randomisation	Randomisation of task order and monitor trend scenario: increasing/decreasing
Timing control task	To assess baseline time perception for each participant
Break	To reset and brief the participant for the first task
First task	Administrative or technical task depending on randomisation

Monitor scenario in first task	The parameters do not change aside from a brief desaturation at 30 seconds into the task, to orient participants to the monitor within the task
Break	To reset and brief the participant for the second task
Second task	Administrative or technical task depending on randomisation
Monitor scenario in second task	There is a desaturation at 30 seconds as before to orient participants to the monitor within the task. The blood pressure then either falls or rises, depending on the randomisation, settling at the final value at 4 minutes. The change in blood pressure only occurs in the second task so as to allow immediate review of trend awareness, this is not possible to do after the first task without introducing bias in the second task.
Post task review	To check immediate recall of monitor trends in the second task. Asked immediately to reduce the impact of recall/memory bias on the answers.
Questionnaire	Provides quantification of any trend in parameters noticed.
Debrief	To answer queries and identify any areas of participant support required.

Experimental scenarios:

Each participant will undertake the timing control task first and then both the administrative and technical tasks, the order of these determined by the randomisation table.

1. Timing control

The participant sits and is asked to push a foot pedal every 10 seconds with no reference to external timekeeping. This task continues for 6 minutes.

Participants are instructed: "Please press the foot pedal every 10 seconds, trying to be as accurate as possible. The task will last for several minutes."

After 6 minutes the participant will be asked for the time period they believe has elapsed between the first pedal press and the last.

2. Administrative task:

Request investigations for a new admission

Equipment required:

- PIMS-TS investigations pack
- Computer signed in to the EPIC learning environment for a dummy patient
- Simulated bedside monitor
 - Varies observations over time in line with preset programming determined by the study team
- Foot pedal and data recorder for time logging

Setup

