 - Correct identification of no trends in other parameters - reported as proportion of participants correct
 - Accuracy of magnitude recall
 - The blood pressure either falls or rises between a systolic/diastolic (mean) of 70/48 (55) and 90/50 (65).
 - From the position of the x on the linear blood pressure scales we can derive:
 - The accuracy of the initial and final estimates compared with the actual values- reported for each task as the population mean and standard deviation of the percentage errors compared with the actual value.
 - The accuracy of the magnitude of the change, determined through comparing the difference in the estimated initial and final values compared with the actual 20mmHg systolic/ 10mmHg diastolic change for each task. The population mean and standard deviation of the percentage errors compared with the actual change will be reported for each task.
 - We hypothesised that there would be a priming effect following administration of the questionnaire, with participants more likely to attend to blood pressure trends if the questions were asked prior to the second task. We will therefore only ask the questions after the second task. We can then compare between the subgroups, split by which of the tasks was performed second to examine the impact of task type.
 - i.e the questionnaire analysis will have half the n of the overall study
- For the above we can compare subgroups using Fishers exact test.
 - By task order
 - By grade
 - By number of CVCs previously inserted

- By first 25% vs last 25% of participants

STATISTICAL CONSIDERATIONS AND DATA ANALYSIS

Sample size and statistical power

This is a pilot study and as such we do not expect it to be adequately powered to confirm hypotheses but intend that it should be hypothesis generating.

Statistical methods

The population summary statistics detailed above will be calculated using 'SPSS statistics' software with built-in min/max/mean/IQR/SD calculation.

With assumed normally distributed timing data and each participant completing 2 tasks the distributions will be compared with a paired sample t-test for; control vs administrative, control vs technical and administrative vs technical. For subgroup analysis paired or unpaired sample t-tests will be used as appropriate in each case. For the trend perception outcomes, contingency tables will be created for each subgroup and compared using Fishers exact test.

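### The technical-versus-administrative timing comparison is a two-period crossover, but the planned paired t-test leaves any period effect in the error term and so gives up precision

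*Combined protocol and SAP*

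**What the plan says.** Under Experimental scenarios, "Each participant will undertake the timing control task first and then both the administrative and technical tasks", with the order of those two set by the randomisation table. The Randomisation section gives the reason for varying the order: "this is randomised to remove the impact of primacy-recency impacts as well as task training through more practice with the timing apparatus". Allocation uses blocks of 4 within two grade strata.

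The two task periods also differ in content. The Structure table states: "The change in blood pressure only occurs in the second task".

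For the timing data, Statistical methods says that "the distributions will be compared with a paired sample t-test for; control vs administrative, control vs technical and administrative vs technical". Task order appears under Time interval analysis only as one of several subgroup splits of the mean interval, to be examined with paired or unpaired t-tests. No period or sequence term, mixed model or order-adjusted estimate is planned.

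No target sample size, SD, effect size or alpha is given. The staff pool is described thus: "This comprises a pool of around 40 staff members". The study is called a pilot, and the authors write that "we do not expect it to be adequately powered to confirm hypotheses".

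**The concern.** For technical versus administrative this is a two-sequence, two-period crossover, and the contrast carries H_A on a primary outcome. If pedal timing drifts between the first and second task, through practice, fatigue or the changed monitor content, the drift adds to the technical-minus-administrative difference in people who do the technical task second. It subtracts in people who do it first. Randomising the order cancels this in the mean when the orders are equal in number. It does not remove the spread that the two opposite shifts create among the differences. A plain paired t-test treats that spread as random error.

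At stake is precision in a study that has little to spare. An avoidably large standard error makes it easier to conclude that time awareness is preserved during the technical task, and the Outcomes and significance section ties the results to procedure guidelines and staffing.

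**Working it through.** **Plan's own figure.** None; the documents contain no power or sample-size calculation to reproduce.

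**Inputs from the documents.** Two tasks per person in randomised order; blocks of 4 in two strata; a printed list of 20 rows per stratum, which counts to 10 administrative-first and 10 technical-first in each; a pool of about 40.

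**Assumptions, not in the documents.** One summary value in seconds per participant per task; SD of the within-person difference 2 s, free of any period effect; task effect τ = 1 s; period effect π (second period minus first) of 0.2 to 2 s; two-sided 5%; 40 participants, 20 per order, unless stated.

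**Model.** Let d = technical minus administrative. Let nA be the number doing the administrative task first and nT the number doing the technical task first.
- Administrative first: E(d) = τ + π
- Technical first: E(d) = τ − π

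**Plain paired t-test.**
- Bias of the mean difference = π(nA − nT)/n
- Expected sample variance of d = SD² + π² × (4·nA·nT/n)/(n − 1)

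At 20:20 the bias is 0 and the multiplier of π² is (4 × 20 × 20/40)/39 = 40/39 = 1.026. At π = 1 s the variance is 4 + 1.026 = 5.026, so the estimated standard error is √(5.026/40) = 0.354 s. At π = 2 s it is √((4 + 4.103)/40) = 0.450 s.

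**Order-adjusted analysis.** The estimate is the mean of the two order-specific means. Its standard error from the pooled within-order variance is ½√[4 × (1/20 + 1/20)] = 0.316 s, whatever π is. The plain test therefore overstates the standard error by 0.354/0.316 = 1.12 at 1 s and 0.450/0.316 = 1.42 at 2 s.

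**Simulated operating characteristics, 20:20** (rounded; good to about one point):

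| Period effect | Paired t power | Adjusted power | Paired t type I error |
|---|---|---|---|
| 0.2 s | 87% | 87% | 5% |
| 0.5 s | 86% | 87% | 4% |
| 1 s | 81% | 87% | 3% |
| 2 s | 61% | 87% | 0.6% |

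The adjusted analysis holds type I error at about 5% throughout. With 20 participants (10:10), paired-t power is about 47% at 1 s and 25% at 2 s, against 56–57% adjusted.

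**How large can the bias be?** I took every combination of consultants and others that stops at some row of the printed list. The largest imbalance is 4, after exactly 2 consultants and 6 others. With 20 or more participants the worst case is 17 consultants (9:8) plus 6 others (4:2). That gives nA − nT = 3 and a bias of 3/23 = 0.13π. A completed list is exactly 20:20, with no bias.

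**The case against.** The strongest reply is that the harm may be negligible. The period effect is unknown; at 0.2 to 0.5 s the loss is only about 0 to 1.5 points of power, and the larger losses need a period effect equal to or twice the assumed task effect. The design also dampens practice: everyone first does a 6-minute control run (about 360/10 = 36 intended presses) and has a break before each task. The blood pressure drift carries no alarm, and nothing in the documents shows that it alters pedal timing. The study is a declared pilot with no power target to miss, and the order subgroup comparison would reveal a large effect. All of this stands, and it limits the weight of the point. It does not justify leaving the term out: the protocol itself expects order effects, and the subgroup look does not take them out of the main test.

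Two stronger readings are tempting. A reader might infer that the timing estimate is biased by order. The documents do not support that as a general claim, because blocking and the 10:10 list per stratum aim for equal orders. An imbalance needs recruitment to stop mid-block or participants to withdraw; withdrawal is permitted, but no rate is given. A reader might also infer a risk of false positives. With equal orders the error runs the other way: the test rejects too rarely.

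**Conclusion.** The point holds as a loss of precision. With equal orders the paired t-test gives an unbiased estimate with too large a standard error whenever there is a period effect. The size depends wholly on assumed values: under those used here, from almost nothing at 0.2 s to 26 points of power (87% to 61%) at 2 s. Bias is a secondary and small matter for anyone following the printed list to 20 or more participants; smaller numbers or uneven withdrawals could make it larger.

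The figures assume one difference per participant. The plan is unclear here: Time interval analysis describes testing each individual's intervals, while Statistical methods reads as a test across participants. For a hypothesis-generating pilot this is a worthwhile refinement, not a threat to validity.

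**What to change.** State in Statistical methods that each participant contributes one technical-minus-administrative difference. Estimate the task effect as the unweighted average of the two order-specific mean differences, with the pooled within-order variance and n − 2 degrees of freedom. An equivalent for complete data is a mixed model with task and period as fixed effects, grade included as the stratification factor, and participant random. Report this as the H_A result with its confidence interval, and show the period estimate beside it.

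The cost is one degree of freedom and a few lines of text, with no new data. Two limits should be written down. The adjustment removes an additive period effect only; if the second-period drift affects the two tasks differently, that interaction remains. It also does nothing for control versus administrative or control versus technical: control always comes first, so those comparisons stay confounded with period.

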 - The trend in monitored observations- increasing or decreasing blood pressure in the second task

The following parameters are measured during both tasks:

- Timestamps of foot pedal use by the participant
- Retrospective recall of total elapsed time
- Time to complete task/progress at experiment end
- Question responses

Following completion of the tasks the data collected can be analysed as below.

Time interval analysis:

- Intervals between pedal presses are extracted for each scenario (timing control/administrative/technical tasks)
 - Derive: min/max/mean/interquartile range/standard deviation for each case
- Comparison of the individual’s retrospective perceived elapsed time with actual elapsed time. Reported as percentage error of actual elapsed time.

This will allow the following results to be reported:

- Mean deviation for each individual from their baseline in each of the tasks.
- Change in retrospective perceived elapsed time compared to actual elapsed time.
- Distribution of timing in the control task for each individual.
- Paired t-test comparison to test if there are significant differences in time interval distribution for each individual between control, administrative and technical tasks.
- Overall proportion of participants showing significant deviation from their own baseline in each of the administrative and technical tasks
- Population limits/mean
- Comparison of the mean perceived time interval between subgroups
 - By task order

- By time within task (split into thirds- 2 minutes each)
- By grade
- By number of CVCs previously inserted
- By first 25% vs last 25% of participants

Monitor trend perception analysis:

Each participant will provide question answers from immediately after the second task.

This will allow the following results to be reported:

- Rationale
 - The first question “Did you see anything of note on the monitor” is chosen to highlight inattentive blindness and is asked immediately to avoid any impact from the role of memory or priming from other questions asked.
 - This will be reported as proportion who noted a change
 - The subsequent questions are asked to elicit responses from those who observed the trend but are not sufficiently confident in their recall to report it.
- From the responses the following can be derived:
 - Correct identification of the blood pressure trend- reported as proportion of participants correct

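### Timing outcome: the aim asks whether role or experience changes the task effect, but the subgroup analysis compares raw mean intervals instead of within-person task differences

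*Combined protocol and SAP*

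**What the plan says.** The third item under Aim(s) of Study is "To examine if the extent of these effects (if any) are affected by clinician role and/or experience". The effects meant are those of task type and loading on attention and on time perception. The single secondary outcome is worded more loosely: "Impact of experience on time perception and monitoring changes".

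Experience is recorded under Study Population as job title and as "Number of CVCs that they have previously inserted - <10, 10-50, >50", which gives three ordered bands.

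The Time interval analysis list includes "Comparison of the mean perceived time interval between subgroups", broken down by grade and "By number of CVCs previously inserted", among other factors. For the test, Statistical methods says: "For subgroup analysis paired or unpaired sample t-tests will be used as appropriate in each case". The same list also promises "Mean deviation for each individual from their baseline in each of the tasks", which the timing control task makes possible. That quantity is not named as the variable for the subgroup comparison.

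The monitoring outcomes are handled separately: "For the trend perception outcomes, contingency tables will be created for each subgroup and compared using Fishers exact test".

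No interaction term, ANOVA, trend test or regression is mentioned. No sample size, significance level or set of CVC contrasts is stated. The sample-size section describes the study as a pilot meant to generate hypotheses.

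**The concern.** Whether the extent of a task effect depends on experience is a question of effect modification. It concerns how the technical-versus-administrative contrast varies between people with more and less experience. A difference between subgroups in mean interval answers another question, namely whether experienced and inexperienced clinicians press the pedal at different rates. People differ in their internal clock whatever the task, and the protocol acknowledges this by running a baseline timing task.

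If consultants and fellows differed on raw intervals, a reader could take it as evidence that experience protects against loading, when it may show only a general difference in pace. Conversely, a real difference in task effect could be cancelled by an opposite difference in pace. The protocol's closing section ties the results to staffing and supervision during procedures, so misattributing the source of a difference would matter even in a pilot.

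The three CVC bands add a smaller difficulty. A t-test compares two groups, so the named method needs either several pairs or a merge of bands that the plan does not specify, and both disregard the ordering.

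**Working it through.** The plan gives no figure to reproduce. The check is algebraic, followed by an illustration with assumed values.

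**Algebra.** Let person i have clock speed u_i. Write the mean intervals as A_i = u_i + a_i (administrative) and T_i = u_i + a_i + τ_i (technical), plus error, where a_i is that person's departure from baseline in the administrative task and τ_i is the task effect. Between two experience groups:
- difference in raw technical mean = Δu + Δa + Δτ;
- difference averaged over both tasks = Δu + Δa + Δτ/2;
- difference in T − A = Δτ.

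Only the last isolates what the aim asks. Subtracting the control-task mean C also removes u, and (T − C) − (A − C) = T − A, so the plan's deviations from baseline already contain it.

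**Inputs.** From the documents: a pool of around 40 staff and three CVC bands. Assumed, because the documents are silent: two-sided 0.05 per test, N of 20 to 40, between-person SD 1.5 s, and SD 1.0 s within person and task.

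**Two groups (such as grade), equal split.** SD of a raw task mean = √(1.5² + 1.0²) = 1.80 s. SD of T − A = √(1.0² + 1.0²) = 1.41 s. Noncentrality = shift / (SD × √(2/n)), with n per group.

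*Common shift of 1.5 s in both tasks, Δτ = 0:*
- n = 10: 1.5 / (1.80 × √0.2) = 1.86, so the raw technical mean is significant in 42% of studies.
- n = 20: 1.5 / (1.80 × √0.1) = 2.63, giving 73%.
- T − A: 5% at both sizes, because there is nothing to detect.

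*Shift of 1.5 s cancelled in the technical task by Δτ = −1.5 s:*
- Raw technical means are equal, so that test rejects in 5%.
- T − A: noncentrality 1.5 / (1.41 × √0.2) = 2.37, power 61% at n = 10; 3.35 and 90% at n = 20.

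**Three CVC bands (20,000 simulated studies per setting; mean task effect 1.0 s; steps of 0.75 s per band).**

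| Truth | Analysis | 7/7/6 | 6/14/20 | 14/13/13 |
|---|---|---|---|---|
| Shift in both tasks, no modification | any of three t-tests on technical mean | 37% | 51% | 60% |
| Same | linear trend in T − A | 5% | 5% | 5% |
| Modification present, technical means equal | any of three t-tests on technical mean | 12% | 12% | 13% |
| Same | linear trend in T − A | 43% | 66% | 77% |

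Running a paired t-test separately within each band does not help. With the same true effect in every band, some bands are significant and others not in 66% to 80% of simulated studies.

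**Secondary arithmetic, illustrative only.** Three independent tests at 0.05 give 1 − 0.95³ = 14.3%. Pairs that share groups give about 12% by simulation. Power on a unit-SD outcome:

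| Band sizes, true pattern (SD units) | Bonferroni pairs | Linear trend | One-way ANOVA |
|---|---|---|---|
| 5/7/8; 0, 0.4, 0.8 | 16% | 26% | 19% |
| 10/15/15; 0, 0.4, 0.8 | 34% | 49% | 38% |
| 10/15/15; 0, 0.8, 0.8 (plateau) | 42% | 41% | 45% |
| 10/15/15; 0, 0.8, 0 (middle only) | 50% | 4% | 55% |

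**The case against.** Four points can be made for the plan.

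1. The secondary outcome can be read as including a main effect of experience on time perception, and comparing raw means does address that reading. This stands. The mismatch is with the third aim, which refers to the extent of the effects.

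2. Baseline-corrected values are already derived, and the phrase leaving the choice of t-test open could allow them to be used. This stands in part. The ingredients exist, but the only subgroup comparison written down is of the mean interval, so the stated rule should be changed and not left to interpretation.

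3. The study is a hypothesis-generating pilot, so control of error across exploratory subgroups carries little weight. This stands for multiplicity. It does not excuse estimating a different quantity, since a pilot also needs an estimate of the effect it asks about.

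4. A linear trend test is not always better. This stands too: its advantage depends on a roughly linear effect, disappears under a plateau, and turns into a large loss if only the middle band differs.

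A reader might also infer that the plan relies on t-tests throughout. It does not: Fisher's exact test is named for the monitoring outcomes, and it accepts a three-level table. Another tempting inference is that three unadjusted pairwise tests are planned and that the secondary outcome carries a 12% false-positive rate. The documents never say which CVC contrasts will be run. Bands might be merged, and the secondary outcome also covers the monitoring results, so that figure is not the outcome's error rate.

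**Conclusion.** The point holds for the timing outcome. The aim calls for effect modification, the stated subgroup comparison is of raw mean intervals, and the algebra shows that this comparison cannot separate clock speed from task effect. That conclusion needs no assumed numbers.

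The size does. With the assumed SDs and a 1.5 s common shift, false suggestion of effect modification runs from 42% to 73% for two equal groups, against 5% with the within-person difference. A smaller common shift or a smaller between-person SD would change these figures. The multiplicity and trend-power figures are illustrations only, because the plan states no N, no significance level and no set of CVC contrasts.

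The point does not extend to trend perception. Those questions are asked once, after the second task, so no within-person task difference exists there. Given the pilot status, this is a worthwhile but minor improvement.

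**What to change.** In Time interval analysis and Statistical methods, state that the experience analyses of timing use each participant's technical-minus-administrative difference in mean interval as the outcome, with each task's deviation from the control task reported alongside.

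- **Grade:** compare this difference between consultants and others by an unpaired t-test, or by a regression that includes task order.
- **CVC bands:** fit one regression or one-way ANOVA of the same difference on the three bands, with task order in the model, in place of separate t-tests. CVC band is not a randomisation stratum, so order may be unbalanced across bands. An ordered score (0, 1, 2) is an option if chosen in advance.
- **Reporting:** give estimates with confidence intervals, labelled exploratory. If raw mean intervals by subgroup are kept, describe them as differences in general pace.

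The cost is analysis wording only; all the data are already collected. The small downside is that a linear score loses its advantage if the effect plateaus and is weak if the effect is not monotone. Using the bands as unordered categories avoids this, at some loss of power when the effect is linear. The Fisher analyses of trend perception are unaffected.

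### For the two-group task-order (H_B) comparison, Fisher's exact test is valid but conservative; Boschloo's exact test would hold 5% and recover some power at little cost

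*Combined protocol and SAP*

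**What the plan says.** The Hypothesis section states H_B with a direction: "In the technical task clinician awareness of monitoring trends is impaired compared to in the administrative task". Accuracy of trend recall is one of the two primary outcomes.

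The trend questions are put once per person, after the second task, so H_B is tested between participants. The Monitor trend perception analysis section says "We can then compare between the subgroups, split by which of the tasks was performed second to examine the impact of task type", and adds "i.e the questionnaire analysis will have half the n of the overall study". It names the test: "For the above we can compare subgroups using Fishers exact test". The comparisons listed are task order, grade, number of CVCs inserted, and first versus last quarter of participants. Statistical methods repeats the choice: "contingency tables will be created for each subgroup and compared using Fishers exact test". No other test is named for these proportions.

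On numbers, Study population says "This comprises a pool of around 40 staff members", and nobody may be recruited twice. Task order is randomised in blocks of 4 within two grade strata. No target sample size, alpha or sidedness is given. The sample size section says of the study that "we do not expect it to be adequately powered to confirm hypotheses but intend that it should be hypothesis generating".

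**The concern.** Fisher's test conditions on the total number of participants who noticed the trend. The design does not fix that total; it fixes, approximately, only the number in each task order. Given the total, a small table has few attainable p-values, and they can jump from far below 5% to above it. A test carried out at a nominal 5% then rejects a true null much less often than 5% of the time, and power falls with it.

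This outcome has little power to spare. It is primary, it is measured once per person, and it comes from a capped pool, so lost power cannot readily be bought back by recruiting more people. The Outcomes and significance section links a significant result to procedure guidelines and to the need for an assistant, so a missed difference would matter.

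**Working it through.** The plan gives no size or power figure to reproduce.

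**Inputs from the documents.** Fisher's exact test; two groups defined by which task came second; a pool of about 40, so at most about 40/2 = 20 per group.

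**Inputs assumed.** 10 to 20 per group (20 to 40 recruits); two-sided 5%; proportions noticing of 80% v 40%, 70% v 30% and 80% v 30%. An unfinished block of 4 can leave a difference of up to 2 in each of two strata, so slightly unequal groups were included.

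**Fisher.** With a of n1 and b of n2 noticing, and t = a + b:

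P(a | t) = C(n1,a) × C(n2,t−a) / C(n1+n2,t)

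The two-sided p-value sums this over all tables no more probable than the one observed.

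*Example, 8/10 v 3/10 (t = 11).* One tail is [C(10,8)C(10,3) + C(10,9)C(10,2) + C(10,10)C(10,1)] / C(20,11) = (5400 + 450 + 10)/167960 = 0.0349. Doubled by symmetry, p = 0.070. The next more extreme table, 9 v 2, has p = 2 × 460/167960 = 0.0055. Nothing lies between, so when 11 people notice, the nominal 5% test runs at 0.55%.

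**Boschloo.** Fisher's p-value is used as the statistic:

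p_B = max over π of Pr(Fisher p ≤ observed Fisher p), with both groups binomial with probability π

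For 8/10 v 3/10, p_B = 0.041. Because p_B cannot exceed Fisher's p, every table that Fisher rejects is also rejected by Boschloo.

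**Size and power.** Size is the maximum over π of the total probability of the rejected tables. Power is the same sum at the two assumed proportions. All tables were enumerated.

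| Groups | Max size, Fisher | Max size, Boschloo | Power 80 v 40, Fisher → Boschloo | Power 70 v 30 |
|---|---|---|---|---|
| 10 v 10 | 1.3% | 4.2% | 25% → 43% | 24% → 42% |
| 9 v 11 | 2.8% | 4.2% | 33% → 39% | 30% → 42% |
| 15 v 15 | 1.8% | 4.3% | 45% → 60% | 43% → 59% |
| 18 v 20 | 3.5% | 4.7% | 68% → 75% | 66% → 70% |
| 20 v 20 | 2.5% | 4.6% | 65% → 73% | 60% → 71% |

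In unequal rows the smaller group has the higher proportion.

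- **Size.** Over equal groups of 10 to 20, Fisher's maximum size runs from 1.3% (10) to 2.9% (13 and 18), and Boschloo's from 4.0% to 4.9%.
- **Gain in power.** Over the same groups, for 80 v 40 and 70 v 30, the gain runs from 49.4 − 46.1 = 3.3 points (13 per group) to 41.8 − 24.3 = 17.5 points (10 per group). For 80 v 30 at 10 v 10 it is 62.2 − 42.6 = 19.6 points.
- **Where it is smaller.** For 80 v 30 at 19 v 19 it is 87.6 − 85.2 = 2.4 points. For 80 v 40 at 18 v 20, with the higher proportion in the group of 20, it is only 69.7 − 68.9 = 0.8 points.
- **Where there is none.** At 5 v 5, the first and last quarters of 20 participants, the two tests reject the same tables. Power for 80 v 30 is 24% with either.

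**The case against.** The strongest reply is that nothing here is wrong. Fisher's test holds its level, suits sparse tables, and choosing a conditional exact test is a recognised position. The plan disclaims adequate power and sets no alpha or decision rule, so a loss measured against 5% is a loss against a threshold the documents never state. H_B is also directional. One-sided Fisher at 5% and 10 v 10 already has 62% power for 80 v 30, the figure that two-sided Boschloo reaches, so leaving sidedness open matters at least as much as the test.

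Most of that stands. It makes this an improvement, not a fault, and it is why alpha and sidedness belong in the fix. It does not remove the gain: one-sided Boschloo in the same case has 73%.

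A reader might also infer more than the documents support:

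- *That every trend comparison is affected.* CVC experience has three categories, so the two-group test does not cover it; very small early/late splits show no gain; and the grade split cannot be sized from the plan.
- *That the test runs at about 1%.* That describes 10 v 10, close to the worst case. A small imbalance raises it to 2.8% at 9 v 11 and 3.5% at 18 v 20.
- *That a role-stratified mid-p test should be used.* The plan contains no role-stratified test to modify. Mid-p has more than one definition and does not guarantee 5%: unstratified, it reached 5.2% two-sided at 10 v 20 and 5.5% one-sided at 16 per group.
- *That the change is free.* The plan names SPSS, and Boschloo's test may need other software.

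**Conclusion.** The point holds as a cheap improvement to one comparison: the two-group task-order test of the trend-recall proportions. Under two-sided 5% and roughly 10 to 20 per group, Fisher's maximum true size is about 1.3% to 3.5%. Boschloo's is higher but still below 5%, and its power is never lower. The gain is about 3 to 20 points in most of the cases examined, and 1 to 2 points in the least favourable.

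Group size, alpha, sidedness and the proportions noticing are all assumptions; only the ceiling of about 20 per group comes from the plan. The change does not make the study well powered: at 10 v 10, power for 80 v 40 is still only 43%.

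**What to change.** In Statistical methods, and where the test is named under Monitor trend perception analysis, add before any data are seen a sentence such as: *For the comparison of trend-recall proportions between participants whose second task was technical and those whose second task was administrative, Boschloo's exact unconditional test will be used at [alpha], [one- or two-sided], with Fisher's p-value as the ordering statistic; Fisher's exact p-value will also be reported.* Naming the ordering statistic matters because two-sided versions can differ when groups are unequal.

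Keep Fisher's test for the three-category CVC comparison and for very small splits such as first versus last quarter. Do not add a stratified mid-p test.

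The cost is one sentence, a decision on alpha and sidedness, and possibly one analysis outside SPSS. No extra participants or data are needed.
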